Title page:

Protocol Title: Functional sucrase deficiency in short bowel syndrome patients with intestinal failure

eProst Number: 20191253
Protocol Version Number: 2
Protocol Version Date: 2/6/2020
PI Name: [name]
NCT Number: NCT04604275

1) Protocol Title

Functional sucrase deficiency in short bowel syndrome patients with intestinal failure

2) Objectives

Primary Aim:

To determine if sucrase supplementation in intestinal failure resulting from short gut syndrome will improve carbohydrate malabsorption, reducing symptoms such as bloating, diarrhea and abdominal pain and thus improve patient's ability to advance enteral nutrition in short gut syndrome patients.

Secondary aim:

To determine if reduced bowel mass/length that occurs in short gut syndrome results in decreased functional sucrase levels and thus disaccharide malabsorption causing symptoms such as bloating, diarrhea and abdominal pain and/or resulting in inability to advance enteral nutrition.

3) Background

Short gut syndrome patients have decreased production of disaccharidases, like sucrase, due to loss of enterocyte mass and thus these patients cannot digest sucrose fully.

The resulting maldigestion of sucrose causes abdominal distension, vomiting and diarrhea that limits the advancement of enteral nutrition in short gut syndrome patients with intestinal failure

The administration of exogenous sucrase will improve sucrose digestion and thus the advancement of enteral nutrition in short gut syndrome patients with intestinal failure.

Sucrose digestion:

Carbohydrates in the diet provide the major exogenous source for glucose, which is the primary energy source for cells. They account for 40-60% of the calories in the western diet and higher percentages in protein scarce diets.

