Placebo-controlled design was chosen because when they are utilized with randomization, they allow for valid treatment group comparisons. The disadvantage of parallel designs is that they can require large sample sizes due to the existence of both within- and between-subject variation. Cross over studies generally require fewer participants than parallel designs because each participant serves as his/her own control, thus eliminating inter-participant variation. Secondly, researchers can study individual participant response to treatment and examine participant-by-treatment interactions. Lastly, study recruitment may

be enhanced as potential participants are aware that they will receive active treatment at some point during the study.

[figure not shown]
c) End of study definition

End of study will occur once all participants have undergone both intervention and placebo arm of the study. Each subject will be enrolled for study period of 9 weeks.

6) Arms and Interventions

Study Arm Description

**FUNCTIONAL SUCRASE DEFICIENCY IN SHORT BOWEL SYNDROME PATIENTS
WITH INTESTINAL FAILURE**

Patients meeting inclusion criteria will be enrolled in the study and will provide written consent in keeping with regulations of the IRB.

Once enrolled “subjects” will be observed for 1 week on their current care and we will record:

Record daily:

Stool frequency and consistency

Side effects on sucrase – blood sugar checks by finger stick and any new symptoms – nausea, headache, etc

Emesis

Record weekly:

Ability to advance feeds

Abdominal circumference

Weight

Patient or parent perception of tolerance of feeds on sucrase by telephone questionnaire

**FUNCTIONAL SUCRASE DEFICIENCY IN SHORT BOWEL SYNDROME PATIENTS WITH
INTESTINAL FAILURE**

DAILY RECORD FOR EACH WEEK

	DAY 1	DAY 2	DAY 3	DAY 4	DAY 5	DAY 6	DAY 7
STOOL FREQUENCY							
STOOL CONSISTENCY							
SUCRASE SIDE EFFECTS							
HEADACHE (YES/NO)							
NAUSEA (YES/NO)							
ABDOMINAL PAIN (YES/NO)							
VOMITING (YES/NO)							
BLOOD SUGAR							

WEEKLY RECORD (EXCEPT WASH OUT WEEK)

	WEEK 1	WEEK 2	WEEK 3	WEEK 4
ABILITY TO ADVANCE FEEDS				
ABDOMINAL CIRCUMFERENCE				
WEIGHT				

	WEEK 6	WEEK 7	WEEK 8	WEEK 9
ABILITY TO ADVANCE FEEDS				
ABDOMINAL CIRCUMFERENCE				
WEIGHT				

**FUNCTIONAL SUCRASE DEFICIENCY IN SHORT BOWEL SYNDROME PATIENTS WITH
INTESTINAL FAILURE**

TELEPHONE QUESTIONNAIRE

	WEEK 1	WEEK 2	WEEK 3	WEEK 4	WEEK 6	WEEK 7	WEEK 8	WEEK 9

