In the treatment arm of the study, subjects we will give sucrase at standard dose, 1 mL (8,500 I.U.) (one full measuring scoop or 28 drops) per meal or snack for patients up to 15 kg in body weight. 2 mL (17,000 I.U.), for a total of 4 weeks and follow patients recording stool frequency and consistency, emesis, weight, ability to advance enteral nutrition. Possible adverse effects of sucrase administration will also be recorded in addition to parental or patient perception of tolerance of feeds while on sucrase.

Give sucrase by g-tube or orally for 4 weeks

Record daily:

Stool frequency and consistency

Side effects on sucrase – blood sugar checks by finger stick and any new symptoms –
nausea, headache, etc

Emesis

Record weekly:

Ability to advance feeds

Abdominal circumference

Weight

Patient or parent perception of tolerance of feeds on sucrase by telephone questionnaire

ONE WEEK WASH OUT – no recordings

Give placebo by g-tube or orally for 4 weeks

Record daily:

Stool frequency and consistency

Side effects on sucrase – blood sugar checks by finger stick and any new symptoms –
nausea, headache, etc

Emesis

Record weekly:

Ability to advance feeds

Abdominal circumference

Weight

Patient or parent perception of tolerance of feeds on sucrase by telephone questionnaire

Possible additional tests:

Some patients will undergo blood test for genetic testing if available, those who have been scheduled for an endoscopy, for other medically indicated reasons as decided by the medical team, will have biopsies taken to rule out CSID.

Patients who consent to breath test for functional sucrase deficiency will have testing done.

Procedures:

SucraID™ (sucrase) administration:

Subject will be asked to take sucrase either orally or through g-tube with feeds daily and will be provided with this medication at no cost. Subjects will take sucrase or placebo each for 4 weeks so they will be taking additional medication daily for 8 weeks as they participate in the study.

Sucrose breath test:

This is an optional test for children over 4 years old that can cooperate by drinking a solution containing sucrose (sugar water) and breathing into a device to record components of their breath. The test will be offered free of charge to subjects in the study. This test is performed at home and the kit can be mailed back to us. The mailing costs are pre-paid. Inability to perform breath test will not eliminate subject from the study.

Endoscopy:

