Endoscopies are often performed to assess patients with short bowel syndrome with intestinal failure who are not progressing as expected. They are done to check for many things, such as, bacterial overgrowth in the intestine, inflammation in the intestine, loss of intestinal cell function, infections in the intestines etc. If a subject has had an endoscopy (obtained for clinical reasons), we will ONLY access these results for research purpose. If subject has not had an endoscopy one will only be performed if clinically indicated by medical team – we will not take additional biopsies or ask for additional tests at the time of endoscopy.

Telephone surveys:

We will conduct short telephone surveys of subject's symptoms while participating in the study. This would be similar to the phone calls they receive from the intestinal rehabilitation team about their feeds, stools, and other associated symptoms.

Medical chart review:

We will also look at recent growth chart in medical record to check growth before and during the study period, we will ask the parent or home nurse to measure abdominal circumference, weight and to check subject's blood sugars at home.

8) Outcome measures

Primary outcomes:

- Outcome Measure Title: Change in Carbohydrate Malabsorption
Outcome Measure Description: Degree of carbohydrate malabsorption will be assessed by decrease in number of stools per day.
Outcome Measure Timeframe: Baseline to Week 9
- Outcome Measure Title: Change in Carbohydrate Malabsorption
Outcome Measure Description: Degree of carbohydrate malabsorption will be assessed by change in patient symptomatology by change in score on patient symptom survey.
Outcome Measure Timeframe: Baseline to Week 9
- Outcome Measure Title: Change in Carbohydrate Malabsorption
Outcome Measure Description: Carbohydrate malabsorption will be measured by increase in growth velocity in kg/week
Outcome Measure Timeframe: Baseline to Week 9
- Outcome Measure Title: Change in Carbohydrate Malabsorption
Outcome Measure Description: Carbohydrate malabsorption will be measured by ability to advance enteral nutrition in ml/day
Outcome Measure Timeframe: Baseline to Week 9

Secondary outcomes

- Outcome Measure Title: Improved Digestion
Outcome Measure Description: Improved digestion will be measured by decreased abdominal distension/girth measured in cm
Outcome Measure Timeframe: Baseline to Week 9
- Outcome Measure Title: Improved Digestion

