Outcome Measure Description: Improved digestion will be assessed by number of emesis per day
Outcome Measure Timeframe: Baseline to Week 9
- Outcome Measure Title: Improved Digestion
Outcome Measure Description: Improved digestion will be assessed by change in stool consistency from hard to formed to semi solid to liquid with pieces to only liquid observed daily
Outcome Measure Timeframe: Baseline to Week 9

9) Adverse Events

a) Definition of AEs

Reported adverse events are minor and rare with Sucraid (sucrase) and overdose has not been described. In clinical studies the adverse experiences were as follows: abdominal pain, vomiting, nausea, diarrhea, constipation, insomnia, headache, nervousness, and dehydration.

b) Definition of SAEs

In one study, one asthmatic child experienced a serious hypersensitivity reaction (wheezing) probably related to sacrosidase. The event resulted in withdrawal of the patient from the trial but resolved with no sequelae.

c) Time Period and Frequency for AE assessment and Follow-up

During weekly phone calls we will assess for worsening symptoms, including but not limited to the AE as listed above

d) Adverse Event Reporting

All adverse events as defined by the FDA will be recorded by study team and reported in the results section of the study and publications.

e) Serious Adverse Event Reporting

All adverse events as defined by the FDA will be recorded by study team and reported in the results section of the study and publications. Subjects will be withdrawn as necessary if SAE occurs during study period.

10) Data and Specimen Banking

Data will be kept on a secure drive and only be accessed by the study team members. Data will be de-identified prior to data entry.

Specimens taken for pathology (for other medically indicated reasons) will be kept in patients private medical record as usual.

11) Data Management

Statistics will be done in compliance with HIPAA regulations on de-identified data.

Data will be stored on a secure drive and only accessible to study team members during and after the study.

Data will be kept post collection in compliance with regulations.

12) Risks to Subjects

Sucrase may cause a serious allergic reaction.

Blood glucose levels may change after taking sucrase – each patient already has monitor to check daily sugars while on therapy.

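### Abdominal pain and bloating, two of the three symptoms named in the primary aim, have no dependable efficacy record on the printed forms

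*Protocol*

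**What the plan says.** Section 2 sets the primary aim as improving carbohydrate malabsorption, "reducing symptoms such as bloating, diarrhea and abdominal pain", and so helping patients to advance enteral feeding.

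Sections 6 and 7 list what is recorded each day: stools, emesis, and side effects on sucrase, the last described as "blood sugar checks by finger stick and any new symptoms" with nausea and headache as examples. The same list is given for the baseline week, in which subjects "will be observed for 1 week on their current care and we will record", and for the sucrase and placebo periods. Girth, weight, feed advancement and perceived feed tolerance are recorded weekly.

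The daily form in section 6 has a line "SUCRASE SIDE EFFECTS" followed by yes/no rows, among them "ABDOMINAL PAIN (YES/NO)" and "VOMITING (YES/NO)". It has no bloating row. The printed telephone questionnaire has one item, the patient's or parent's view of feed tolerance on sucrase. Its columns are weeks 1 to 4 and 6 to 9.

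Section 8 makes "change in patient symptomatology by change in score on patient symptom survey" a primary outcome, from baseline to week 9. Stools per day is another primary outcome. Girth, daily emesis and stool consistency are secondary outcomes. Section 9 lists the adverse experiences seen with the product: "abdominal pain, vomiting, nausea, diarrhea, constipation, insomnia, headache, nervousness, and dehydration". It says that the weekly calls will look for worsening symptoms.

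**The concern.** A trial that aims to relieve a symptom has to record whether the symptom is present, in the same way before treatment and in each period. For abdominal pain the protocol gives two instructions that do not agree. The form asks whether there was pain that day; the text describes the entry as side effects and new symptoms. A family that follows the text has nothing to enter for pain that was there before the study, so its relief leaves no mark. In the baseline week it is not even clear what new would be measured against. For bloating there is nothing to enter at all.

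This is a matter of data capture, so a statistical analysis plan could not repair it: no analysis recovers a symptom that was not asked about or was left blank because it was not new. Section 20 plans 10 subjects, so a few families reading the form differently would carry weight.

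**Working it through.** The protocol gives no figure on this point, so the check is to follow each symptom in the aim through the forms, the recording text and the outcomes.

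| Symptom in the aim | Daily form | Recording text (sections 6 and 7) | Outcome (section 8) |
|---|---|---|---|
| Diarrhea | Stool frequency and consistency rows | Own daily item | Primary (stools per day) and secondary (consistency) |
| Abdominal pain | Yes/no row after the side-effect line | Only within side effects and new symptoms | None by name; the symptom survey might cover it |
| Bloating | No row | No symptom item; weekly girth | Girth is secondary; the symptom survey might cover it |

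**The survey.** The only questionnaire printed has one item, on feed tolerance. It has no pain item, no bloating item and no scoring. Its 4 + 4 = 8 columns match two four-week treatment periods either side of a washout in week 5. On that reading the baseline week has no column, although the outcome is a change from baseline. Section 7 says that the calls will cover symptoms but does not name pain or bloating.

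**Direction of the questions.** The daily text asks for new symptoms and the weekly calls look for worsening. Neither asks whether an existing symptom has eased, which is the aim.

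**What the two readings of the pain row can do.** The figures here are assumed, not taken from the protocol. Suppose a subject has pain on 5 of 7 days at baseline and on placebo, and on 2 of 7 days on sucrase.

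- True change: (5 − 2)/5 = 60% fewer pain days.
- Every pain day entered: placebo 5 × 4 = 20 days, sucrase 2 × 4 = 8 days, difference 20 − 8 = 12 days.
- Only new pain entered: 0 days in both periods, difference 0.
- Mixed use: if all 10 subjects had this pattern and k families entered every pain day while the rest entered only new pain, the mean difference would be 12 × k/10. That is 12 days for k = 10, 6 for k = 5 and 0 for k = 0.

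The recorded effect thus depends on how the form is read as well as on the treatment.

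**The case against.** The other side has several good points.

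- **The pain row does not say new.** A parent who answers it literally records existing pain, and the same items are listed for baseline, sucrase and placebo. A reader might infer that relief of pain cannot be seen at all. The documents do not support that, because literal completion would allow a comparison. What stands is that form and text disagree. The text version of the form also does not show how far the side-effect line extends as a heading.
- **A symptom survey score is a primary outcome.** It may be meant to cover pain and bloating, and the protocol does not say that the printed questionnaire is that survey. But no other instrument is shown and no items are named, so it cannot be relied on to fill the gap.
- **Vomiting.** It shares the yes/no block with pain, so a reader might include it in the defect. It does not belong there: emesis is a separate daily item in every recorded period, daily emesis is a secondary outcome, and the aim does not name vomiting.
- **Harm wrongly charged to the drug.** Pain, vomiting and diarrhea are on the adverse experience list and are also symptoms of the disease or targets of the aim. A reader might infer that disease symptoms will count against sucrase. No passage says so. Recording is the same on placebo, and in the example above 8 days against 20 would read as benefit.
- **Girth and young children.** Subjects of all ages are eligible, and infants cannot report bloating, so girth is a reasonable measure of distension. It is still not the felt symptom that the aim names, and a parent or nurse can record an observed one.
- **Background.** Section 3 describes diarrhea, vomiting and distension as usual in these patients, but not pain. How many subjects start with pain is therefore unknown.

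**Conclusion.** The point holds for abdominal pain and bloating. Two of the three symptoms named in the primary aim lack a dependable efficacy record on the printed forms. Pain has a row, but its use is left in conflict between form and text. Bloating has no symptom row, and the survey that might cover both is not specified. Diarrhea is properly covered.

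The size cannot be taken from the protocol. In the assumed example a 60% fall in pain days appears as anything from a 12-day difference to none, depending on how families complete the row. This matters only to the extent that subjects enter with pain or bloating and that some families follow the text rather than the row. The conclusion is that the records are undependable. It does not extend to saying that benefit is impossible to detect or that harm will be overstated. The change is worth making because it is cheap and has to be made before data are collected.

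**What to change.** 1. On the daily form, move abdominal pain out of the side-effect rows into a block for symptoms present that day, and add a bloating row. Where the child cannot report, the parent or home nurse records what is observed.
2. State in sections 6 and 7 that both rows are completed every day of the baseline week and of both treatment periods, whether or not the symptom is new or thought to be related to treatment.
3. In section 8, name days per week with pain and days per week with bloating as measures for the aim, compared between sucrase and placebo.
4. In section 9, count a symptom as a side effect when it is new or worse than in that subject's baseline week, and apply the same rule in both periods.

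The cost is one extra row, a changed heading and a few sentences of text. The form is already filled in daily, so the only downside is slightly more recording for families and nurses.

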Patient or parent perception of tolerance of feed on sucrase								

POSSIBLE ADDITIONAL TESTING

- Blood test for genetic testing if available.
- If scheduled for an endoscopy, for other medically indicated reasons as decided by the medical team, will have biopsies taken to rule out CSID.
- Breath test for functional sucrase deficiency in patients who consent.

Study Intervention Description

Subjects will be administered sucraind (sucrase) daily as instructed and followed as above. There will be a one week wash out period
During cross over subjects will be administered “placebo” daily as instructed and followed as above.

a) Intervention dosing and administration information

The recommended dosage is as follows: 1 mL (8,500 I.U.) (one full measuring scoop or 28 drops) per meal or snack for patients up to 15 kg in body weight. 2 mL (17,000 I.U.) Dosage

is 1 or 2 mL (8,500 to 17,000 I.U.) taken orally or by g-tube with each meal or snack diluted in water, milk, or infant formula. Half of the dosage will be taken at the beginning of the meal or snack and the remainder be taken during the meal or snack. The beverage or infant formula should be served cold or at room temperature. The beverage or infant formula should not be warmed or heated before or after addition of Sucraid because heating is likely to decrease potency.

b) Study Intervention Compliance

Patients will be called weekly for verification of compliance. Most patients have home nursing so their home nursing records will be reviewed as well. Finally patients will be asked to verify how much medication they have left at end of each week to assess compliance.

7) Procedures Involved

Patients meeting inclusion criteria will be enrolled in the study and will provide written consent in keeping with regulations of the IRB.

Once enrolled “subjects” will be observed for 1 week on their current care and we will record:
Record daily:

Stool frequency and consistency

Side effects on sucrase – blood sugar checks by finger stick and any new symptoms –
nausea, headache, etc

Emesis

Record weekly:

Ability to advance feeds

Abdominal circumference

Weight

Patient or parent perception of tolerance of feeds on sucrase by telephone questionnaire

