Some patients treated with sucrase may have worse abdominal pain, vomiting, nausea, or diarrhea. Constipation, difficulty sleeping, headache, nervousness, and dehydration have also occurred in patients treated with sucrase.

Patients will only undergo endoscopy with biopsy if there is another medical indication as decided by the primary medical team (not the study team). Thus this risk does not pertain to the study.

13) Potential Benefits to Subjects

The most significant sources of morbidity and mortality in children with SBS are catheter related blood stream infections and parenteral nutrition-associated liver disease. Strategies that advance enterally feeding thus eliminating need for parenteral nutrition and thus central venous catheters can significantly improve outcomes in short bowel population.

14) Participant Discontinuation/ Withdrawal from the study

Participants may be discontinued if:

- They have bacteremia during course of study period and require IV antibiotic administration.
- They experience SAE or an AE that prevents them from continuing medication.
- They are admitted to the icu or hospital and made NPO during study period
- They undergo an unplanned surgery or procedure requiring them to be NPO for more than 12 hours
- They are switched by medical team to a diet not containing sucrose.
- They are no longer willing to participate in study

We will attempt to replace the withdrawn participant with another subject.

Any data collected on withdrawn subjects will be removed for purposes of statistical analysis.

15) Vulnerable Populations

NIL

16) Setting

Jackson Memorial Health system/University of Miami

17) Resources Available

[name], Assistant Professor of Pediatrics, Pediatric GI and Nutrition Specialist who runs the nutrition program at UM and Jackson that treats many patients with SBS. She has published articles on topic of SBS.

[name], Assistant Professor of Pediatrics, Pediatric GI and Short Bowel Syndrome Specialist who heads the Intestinal Rehabilitation and Intestinal Transplant service at Jackson and UM. She has published and presented data related to care of SBS for several years in many international meetings.

[name], Professor of Pediatrics, Division Chief of Department of Pediatric GI, well-published, world-renowned Pediatric GI specialist and also prior consultant on use of sucrase in patients with sucrase deficiency.

18) Prior Approvals

NIL

19) Recruitment Methods

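### Sections 6 and 7 stop recording in the washout week while sections 9c to 9e promise weekly adverse-event assessment, so the first week off sucrase has no scheduled safety capture in either order

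*Protocol*

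**What the plan says.** **Washout and forms.** Section 7 lists three steps: "Give sucrase by g-tube or orally for 4 weeks", then "ONE WEEK WASH OUT – no recordings", then "Give placebo by g-tube or orally for 4 weeks". The items recorded daily on either side of the washout include side effects, finger-stick blood sugar, new symptoms and emesis. In section 6 the weekly form is headed "WEEKLY RECORD (EXCEPT WASH OUT WEEK" and has columns for Weeks 1 to 4 and 6 to 9. The "telephone questionnaire" has the same columns. The daily form in section 6 carries no washout exception in its heading.

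**Adverse events.** Section 9c, whose heading covers period, frequency and follow-up, reads: "During weekly phone calls we will assess for worsening symptoms, including but not limited to the AE as listed above". It exempts no week and sets no end to collection. Sections 9d and 9e add that all adverse events will be recorded by the study team.

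**Length.** Section 5c gives 9 weeks of enrolment per subject and ends the study once every participant has been through both arms. No contact after the last dose is stated.

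**Discontinuation.** Section 14 applies its triggers across the whole study period, for example "They have bacteremia during course of study period and require IV antibiotic administration". That period includes the washout.

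**The concern.** Section 7 does not limit its washout rule to efficacy. The daily list that it suspends contains the safety items, so on a plain reading safety recording stops too. A coordinator following section 7 and the printed forms would collect nothing in Week 5. A coordinator following section 9c would make the call but have no column in which to enter the result.

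The week in question is not a neutral one. The Protocol's background attributes diarrhea, vomiting and distension to undigested sucrose, and the trial hopes to advance enteral feeds on sucrase. If the enzyme works as hypothesised, a subject may reach the end of the sucrase period on more enteral feed than before and then lose the enzyme. Subjects depend on parenteral support for at least 50% of fluid or caloric needs (section 4). Vomiting, diarrhea and dehydration are among the adverse experiences listed in section 9a.

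Two things are at stake. One is timely notice of worsening after sucrase is stopped. The other is a tabulation by product that places each event under the right treatment.

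**Working it through.** No sample-size or error-rate formula applies. The check is timeline arithmetic, followed by a comparison of passages.

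**Inputs.** Two periods of 4 weeks and a washout of 1 week (section 7); 9 weeks of enrolment (section 5c); form columns for Weeks 1 to 4 and 6 to 9 (section 6); 10 subjects (section 20).

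**Step 1: reproduce the stated length.** 4 + 1 + 4 = 9 weeks. This matches section 5c, and the form numbering makes the washout Week 5. Sections 6 and 7 also say that subjects "will be observed for 1 week on their current care" on enrolment. Counting that week gives 1 + 4 + 1 + 4 = 10, which does not fit 9. On either count no time is left after the last dose.

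**Step 2: count scheduled recording.** The weekly and telephone forms cover 4 + 4 = 8 of 9 weeks. The gap is 1/9 = 11% of the weeks. Scheduled contact after the last dose is 0 days.

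**Step 3: find the first week off sucrase in each order.**

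| Order | Sucrase ends | First week off sucrase | Scheduled recording if section 7 governs |
|---|---|---|---|
| Sucrase first (as listed in section 7) | End of Week 4 | Week 5, washout | None |
| Placebo first | End of Week 9 | After the study period | None |

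The gap does not depend on the order. This matters because section 5b mentions randomization and the design figure is not shown.

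**Step 4: compare the passages on Week 5.**

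| Source | Week 5 |
|---|---|
| Section 7, washout line | Nothing recorded |
| Section 6, weekly form | Excluded |
| Section 6, telephone form | No column |
| Section 6, daily form | No exception in the heading |
| Section 6b, compliance calls | Weekly, no exception |
| Section 7, telephone surveys | During participation, no exception |
| Section 9c | Weekly calls, no exception |
| Sections 9d and 9e | All adverse events recorded |

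The first three rows cannot all be followed together with the last five.

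**Step 5: what cannot be computed.** The document gives no adverse-event rates, so the number of events missed or misplaced is unknown. For scale only, one subject is 1/10 = 10% of the sample.

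**The case against.** The strongest reply is that safety capture never actually stops. Section 9c exempts no week, and sections 9d and 9e are unqualified. Compliance calls are weekly, home nursing records are reviewed, and telephone symptom surveys run throughout participation. The symptom items sit on the daily form, whose heading makes no washout exception. The telephone form that skips Week 5 has a single row, on perceived tolerance of feeds, and is not shown to be the 9c safety call. Events such as bacteremia or a hospital admission would reach the clinical team without a study call.

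Much of this stands. A reader might infer that events just after stopping sucrase will go unrecorded. The text does not support that, because the passages just listed may pick them up and the Week 6 call may do so in retrospect. A reader might also infer that such events will be charged to placebo and make sucrase look safer. No passage assigns washout events to the next product, and the order is not settled by the text at hand. An assignment rule for analysis may also lie in an analysis plan that is not shown.

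The reply does not remove the contradiction with section 7. The passages it relies on are the ones that section 7 conflicts with, and none of them covers the time after the last dose. Nor can an analysis plan recover onset dates that were never collected.

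**Conclusion.** The point holds as an inconsistency in data collection. Sections 6 and 7 contradict sections 9c to 9e on whether adverse events are collected in Week 5. If section 7 governs, 1 of 9 weeks (11%) has no scheduled capture. No contact is stated after the last dose, and so the first week off sucrase is uncovered in both orders, for all 10 subjects.

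This rests on two assumptions: that the washout rule means what it says and is not confined to efficacy, and that the 9-week period is 4 + 1 + 4. Late pickup remains possible. A late report without an onset date could be entered under the second period's product, but neither the direction nor the size of any resulting distortion can be established. The correction is cheap and should be made, since it affects safety capture in a dependent population. The document does not support a claim of demonstrated bias.

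**What to change.** Reconcile sections 6, 7 and 9c to 9e as follows:

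- Limit the washout rule in section 7 to the efficacy items.
- State that the weekly adverse-event call of section 9c continues in Week 5, and add a Week 5 adverse-event column to the form.
- State when adverse-event collection ends after the last dose, for both treatment orders. One further call is a possible way to close the window. The documents do not dictate its timing.
- Record each event's onset date and the last product taken, so that a late report can be placed correctly.

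The cost is a wording amendment and one or two short calls per subject, which is 1 × 10 = 10 to 2 × 10 = 20 calls in all, by a team that already calls weekly.
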